11.3 Ethical Conduct of the Study

This study will be conducted according to ICH and GCP guidelines, and all applicable government regulations and Institutional research policies and procedures.

11.4 Patient Information and Consent

All subjects for this study will be provided a consent form describing this study and providing sufficient information for subjects to make an informed decision about their participation in this study. The formal consent of a subject, using the IRB/IEC-approved consent form, must be obtained before any study procedure is undertaken. This ICF must be signed by the subject or legally acceptable surrogate, and the Investigator or designated research professional obtaining the consent.

The consent form and explanation will include; detailed information about BPS-314*d*-MR, the rationale for why it is being studied, frequency of dosing, and length of treatment, potential side effects and risks, safeguards and emergency procedures. Information will also be provided about the frequency and length of visits. The collection of all lab specimens will be described in detail. Subjects will be assured that their participation is voluntary and that withdrawal from the study would not jeopardize current or future treatment. All subjects will be informed of potential risks and benefits involved in the study, including side effects of BPS-314*d*-MR.

11.5 Patient Confidentiality

Every effort will be made to keep medical information confidential. The Sponsor, appropriate Regulatory Authorities, and the IRB/IEC governing this study may inspect the medical records

of any subject involved in this study. The Investigator may release the subject's medical records to employees or agents of the Sponsor, the IRB/IEC or appropriate regulatory agencies for purposes of checking the accuracy of the data. A number will be assigned to all subjects and any published study reports will not identify subjects.

11.6 Study Monitoring

In accordance with U.S. federal and other national regulations, ICH, and GCP guidelines, monitors for Sponsor or its designee will periodically contact the site and conduct on-site visits. The first monitoring visit will occur within the first few weeks after the first subject's Screening Visit. During these visits, the monitor will at a minimum: confirm ethical treatment of subjects, assess study progress, review data collected, conduct source document verification, verify drug accountability periodically, and identify any issues requiring resolution.

11.7 Case Report Forms and Study Records

The study case report form (CRF) is the primary data collection instrument for the study. For this study, the CRF will be completed electronically. All data requested on the CRF must be recorded following the CRF completion guidelines to be provided to site personnel. Subject data will be entered in the CRF by appropriate site staff. Data recorded in the CRF should be consistent with source documents.

11.8 Oversight Committees

11.8.1 Data Safety Monitoring Board

A Data Safety Monitoring Board (DSMB), independent of the Sponsor, will be established for the study. Operating under a formal charter, the DSMB will be comprised of three members: two physicians knowledgeable in the treatment of PAH and one statistician. Throughout the course of the study the DSMB will meet regularly to monitor the safety of the subjects in the study.

11.8.2 Endpoint Adjudication Committee

The study will have an Endpoint Adjudication Committee (EAC) composed of PAH physicians not otherwise involved in the conduct of the study. The EAC will operate under a formal charter. Throughout the course of the study the EAC will review clinical worsening events (the primary study endpoint). The EAC may meet with frequency based on the rate of enrollment and the rate of occurrence of clinical worsening events.

11.9 Access to Source Documentation

The Investigators agree to allow the monitors direct access to all relevant documents, including electronic records, and the Investigators will allocate their time and staff to discuss any findings or any relevant issues.

11.10 Data Generation and Analysis

All data are submitted into a quality assured database from the site and will be reviewed by the Sponsor. Data clarifications will be generated and the database will be edited as appropriate. The database will be final when all queries have been resolved and all data management quality assurance procedures are complete. A full audit trail of all entries and changes to CRFs will be maintained in the database structure.

11.11 Retention of Data

In accordance with U.S. federal and other national regulations, ICH, and GCP guidelines, the Investigator must retain study records for at least 2 years after the last approval of a marketing application in an ICH region and until there are no pending or contemplated marketing applications in an ICH region or at least 2 years have elapsed since the formal discontinuation of clinical development of the investigational product. The Investigator must notify the Sponsor before any disposal or change in location of study records. The Investigator should ensure that the location considered for archiving study records is an appropriate facility for the secure storage of study documents and records.

11.12 Publication and Disclosure Policy

Manuscripts or abstracts for written or oral presentation by Investigators associated with this study must be submitted to the Sponsor at least 30 working days for approval before submission to any journal or meeting. Scientific comments by the Sponsor should be taken into consideration before submission. The Sponsor reserves the right to request revision of written or oral presentations or to deny such presentations if, in the opinion of the Sponsor, such activity would adversely affect the drug development program.

Appendix 1 Schedule of Events

	Study Visit Week									
STUDY PROCEDURES	Screening ⁹	Baseline Day 1 (3-120 days)	Baseline Day 2	Phone calls	Week 4 (± 3 days)	Week 8 (± 4 days)	Week 12 First Quarterly Visit (± 10 days)	Quarterly Visits (± 10 days)	End of Study or Early Termination Visit ¹⁰	Unscheduled Visit(s) ¹¹
Clinic Site Visit	Х	Х	X		Х	Х	Х	Х	Х	Х
Phone Calls ¹				Х						
Informed Consent	Х									
I/E Criteria ²	Х	Х								
Demographics	Х									
PAH History	Х									
Medical History ³	Х	Х								
Physical Examination	Х	Х			Х	Х	Х	Х	Х	Х
Vital Signs (height at Screening only)	X	Х			Х	Х	X	Х	Х	Х
Clinical Worsening Assessment				X	Х	Х	X	Х	Х	Х
6-Minute Walk Test	Х	X^4	X^4		Х	Х	Х	Х	Х	Х
Borg Dyspnea Scale	Х	Х	Х		Х	Х	Х	Х	Х	Х
WHO Functional Class	Х	Х			Х	Х	Х	Х	Х	Х
Laboratory Parameters	Х	Х			Х	Х	Х	Х	Х	Х
OPTIONAL: Plasma Concentration ⁵					X		Х			Х
OPTIONAL: RHC ⁶		Х						Х		
Pregnancy Test ⁷	Х	Х			Х	Х	Х	Х	Х	Х
12-Lead ECG	X	Х			X	Optional X	Х	Х	Х	Х
Randomization		Х								
Study drug & Tyvaso	Х	Х								
Administration	Tyvaso	Tyvaso	Х	Х	Х	Х	Х	Х		Х
instructions & record ⁸	only	only								
Drug Accountability					Х	Х	X	X	X	X
AE Assessment	X	Х	Х	Х	Х	Х	X	X	X	Х
Conmed Assessment	Х	Х	Х	Х	Х	Х	Х	Х	Х	Х

Phone calls: Between the Baseline Visit and the Week 12 (first Quarterly Visit) subjects should be contacted weekly (except for weeks with study visits), then monthly between Quarterly Visits through the end of study participation.

² Inclusion/Exclusion criteria to be collected at the Screening Visit and updated at the Baseline Visit as needed (Sections 5.2 and 5.3).

- ³ Medical history to include relevant and significant past or present illness or surgeries.
- ⁴ 6MWTs at Baseline (Day 1 and Day 2) should be conducted post-randomization and prior to dosing study drug. 6MWTs at scheduled visits after Baseline should be performed between 1-2 hours, ± 15 minutes, after the second or third dose of inhaled treprostinil. During the run-in period, subjects should be guided through proper up-titration, monitored for appropriate dosing and offered additional training by phone or in-person as needed.
- ⁵ Optional Plasma Concentration Assessment: For the Week 4 Visit collect two 10mL trough (15 minutes pre-dose, ± 5 minutes) samples; for Week 12 (first Quarterly Visit) collect two 10mL samples around the second daily dosing of study drug: 15 minutes pre-dose, and 15 minutes, 1 hour and 2.5 hours post-dose (± 5 minutes); subjects participating in the plasma concentration assessment should be contacted one week (7 days) prior to Week 4 and Week 12 (first Quarterly Visit) as a reminder to record their Tyvaso and study drug dosing times during the week leading up to the visit.
- ⁶ Optional RHC assessment procedures may be conducted up to 21 days prior to the Baseline Visit and at the Month 6 Quarterly Visit (± 7 days). Baseline RHC should be performed prior to study drug dosing. The Month 6 RHC should be performed between 1-2 hours, ± 15 minutes, after the second or third dose of study drug and inhaled treprostinil.
- ⁷ Pregnancy testing for females of childbearing potential. Urine test at Baseline Visit and serum test at all other clinic visits.
- ⁸ All doses of study drug and inhaled treprostinil administered at the study site and all dose changes should be recorded in subject dose administration log.
- ⁹ Subjects who consent to the study but are not currently taking inhaled treprostinil and who otherwise meet study eligibility criteria will enter a run-in period on inhaled treprostinil to achieve 90 days of experience, with 30 or more days at a stable dose, to ensure drug tolerability before being randomized. Subjects who consent to the study and are currently taking inhaled treprostinil at the Screening Visit should be randomized into the study as soon as eligibility criteria have been met. See Appendix 2.
- ¹⁰ When the Sponsor concludes the study or the subject withdraws consent or is terminated from the study, the subject will be required, as applicable, to return to the study site for an End of Study Visit and the Study Termination CRF will be completed.
- ¹¹ An Unscheduled Visit may occur at any time and involve any of the procedures listed as deemed appropriate by the Investigator.

Appendix 2Schematic of Study Entry Based on Tyvaso Use

Eligibility for the study is available to PAH patients regardless of their current Tyvaso use status.

- 1. *Tyvaso Naïve or Inactive* patients who meet candidacy criteria for the study protocol will be initiated on Tyvaso during the screening period, commencing with training and followed by a run-in period. Following completion of the 90 day run-in period, if eligibility is confirmed then patients will be randomized into the study.
- 2. Patients who are *Active Tyvaso Users* at the initiation of screening will continue with their current therapy. It is anticipated that patients will be promptly enrolled in the study as soon as eligibility is confirmed.

Following randomization, study subjects will receive Tyvaso and study drug for the duration of the study with clinical assessments (red diamonds) as identified in the study protocol.

Appendix 3 6-Minute Walk Test Procedures

General Procedures

The administration of the 6-Minute Walk Test and specifications of the testing area should be generally consistent with the American Thoracic Society (ATS, 2002) guidelines and the usual practice of the clinical site.

To the extent possible and to lessen the opportunity for bias, test administrators should not review the subject's prior 6MWT results before conducting the test. When the 6MWT is completed the test administrator *will not* tell the subject the distance walked. Results of the 6MWT should not be provided to the subject during the course of the study.

The area used for the 6MWT should be pre-measured at approximately 30 meters (100 feet) in length and approximately 2 to 3 meters (7 to 10 feet) in width. There should be no turns or significant curves to the 6-minute walk area. The length should be marked with gradations to ensure the accurate measurement of the distance walked. The tester may be at the starting end of the corridor or at the midpoint of the corridor with a stop-watch. Intermittent rest periods are allowed if the subject can no longer continue. If the subject needs to rest briefly, he/she may stand or sit and then begin again when he/she is sufficiently rested but the clock will continue to run. At the end of 6 minutes, the tester will call "stop" while simultaneously stopping the watch and then measure the distance walked. At any point in the trial, if a subject is assessed for the 6MWT while using oxygen therapy then all future 6MWTs should be conducted in the same way with the same oxygen flow.

Instructions to the Subject

Subjects should be told to wear comfortable clothing and sneakers or comfortable walking shoes. The person administering the test will use the following exact dialogue with the subject:

"The purpose of this test is to find out how far you can walk in six minutes. You will start from this point and follow the hallway to the marker (e.g., chair) at the end, turn around and walk back. When you arrive back at the starting point you will go back and forth again. You will go back and forth as many times as you can in the 6-minute period. You may stop and rest if you need to. Just remain where you are until you can go on again. However, the most important thing about the test is that you cover as much ground as you possibly can during the six minutes. I will tell you the time, and I will let you know when the 6 minutes are up. When I say STOP, please stand right where you are."

After these instructions are given to the subject, the person administering the test will then ask:

"Do you have any questions about the test?"

"Please explain to me what you are going to do."

The person administering the test will then start the test by saying the following to the subject:

"Are you ready?"

"Start when I say "GO."

The person administering the test will tell the subject the time at 2 and 4 minutes by saying:

"You have completed 2 minutes."

And then by saying:

"You have completed 4 minutes."

No other instruction or encouragement will be given during the test. Eye contact with the subject should be avoided during the test.

Appendix 4 Borg Dyspnea Scale

Immediately following the 6MWT, the person administering the test will obtain a rating of dyspnea using the Borg Scale. The person will use the following dialogue:

"I would like to use the following scale to indicate the maximal shortness of breath you had during the walk test (indicate the Borg Scale). If there was no shortness of breath at all you would point to 0; if the shortness of breath was not very great you would choose from 0.5 to 2; if you were somewhat more short of breath you would select 3; and if the breathing was getting very difficult, you would choose 4 to 9, depending on just how hard it was; 10 represent the greatest shortness of breath you have ever experienced in your life. If one of the numbers does not exactly represent how short of breath you are, then you can choose a fraction between. For example, if you had shortness of breath somewhere between 4 and 5, you could choose 4 ½."

Perceived Breathlessness (Borg Scale)

- 0 NOTHING AT ALL
- 0.5 VERY VERY SLIGHT (just noticeable)
- 1 VERY SLIGHT
- 2 SLIGHT
- 3 MODERATE
- 4 SOMEWHAT SEVERE
- 5 SEVERE
- 6
- 7 VERY SEVERE
- 8
- 9 VERY VERY SEVERE (almost maximum)
- 10 MAXIMUM

Appendix 5 WHO Functional Classification for PAH

Class I - Patients with pulmonary hypertension but without resulting limitation of physical activity. Ordinary physical activity does not cause undue dyspnea or fatigue, chest pain, or near syncope.

Class II - Patients with pulmonary hypertension resulting in slight limitation of physical activity. These patients are comfortable at rest, but ordinary physical activity causes undue dyspnea or fatigue, chest pain or near syncope.

Class III - Patients with pulmonary hypertension resulting in marked limitation of physical activity. They are comfortable at rest. Less than ordinary activity causes undue dyspnea or fatigue, chest pain, or near syncope.

Class IV - Patients with pulmonary hypertension with inability to carry out any physical activity without symptoms. These patients manifest signs of right heart failure. Dyspnea and/or fatigue may be present even at rest. Discomfort is increase by any physical activity.

Appendix 6 Plasma Concentration Samples: Handling and Shipping

BPS-314d-MR and Tyvaso® (Treprostinil, inhaled)

Blood Sample Collection and Processing

Detailed instructions for collection and processing will be specified in the Study Reference Manual. General instructions are as follows:

Sample Collection and Processing Instructions

For the Week 4 blood collection time point, collect 2 (two) 10mL blood samples at study drug trough(15 minutes pre-dose, \pm 5 minutes) in a chilled, lavender-topped evacuated tube containing **K2EDTA** as an anticoagulant and immediately place the sample on ice.

For Week 12 (first Quarterly Visit), collect 2 (two) 10mL blood samples in chilled, lavendertopped evacuated tubes containing **K2EDTA** as an anticoagulant and immediately place the sample on ice. Samples should be collected around the second daily dosing of study drug: 15 minutes pre-dose, and 15 minutes, 1 hour and 2.5 hours post-dose.

The samples should be kept cold throughout all handling procedures. 1 (one) tube is collected for BPS-314*d*-MR analysis and another one for treprostinil analysis.

Within 15min after drawing the blood, centrifuge the sample at 4 °C for 15 minutes at 3000x g. There should be approximately 6mL of plasma per each full 10mL blood draw.

Pipette four (4) **EQUAL** aliquots of plasma into four (4) cryotubes of an appropriate size and labeled as A, B, C, D. Keep all cryotubes on ice until frozen. Once frozen place into freezer: either -20°C or -70°C. Samples A and B will be labeled as BPS samples. Samples C and D will be labeled as treprostinil samples.

Plasma Sample Shipment

Plasma samples from each cohort will be sent as two batches on separate days to Intertek Pharmaceutical Services. Samples A and C tubes will be packed in dry ice and shipped on a Monday; samples B and D tubes will be packed in dry ice and shipped on a Tuesday to Intertek for laboratory analysis. Shipping tubes should be individually packaged to prevent breaking and contamination of other samples. Plasma samples will be packed in Styrofoam boxes containing a generous supply of dry ice for 2-3 days in-transit.

All shipments must be accompanied by a packing list.

Prior to shipment of samples, the site will contact the sponsor-designated laboratory by fax or email. An advance electronic copy of the packing list will be provided to

The shipping address and contact information for

Appendix 7 Adverse Events

The Investigator or designee will probe each subject for any adverse events which may have occurred. When possible, always ask the same question when conducting the verbal probe in order to ensure uniformity between subjects. The subject should be asked:

"How have you been doing (feeling) since your last visit?" "How are you doing (feeling) now?"

Based on the subject's response to these questions, the subject should be asked additional questions relevant to any specific complaint such as:

"Have you had this symptom in the past?"

"How severe is/was the symptom?"

"How often did the symptom occur?"

"How long did the symptom last?"

"Did you take any medication to treat the symptom?"

"Did you see a physician or go to the hospital because of this symptom?"

All adverse events should be fully documented on the CRFs.

DEFINITIONS

An **adverse event (AE)** is defined as any untoward medical experience/occurrence associated with the use of a drug in humans, whether or not it is considered drug related. An AE may include an intercurrent illness, injury, or any other concomitant impairment of the subject's health, as well as abnormal laboratory findings if deemed to have clinical significance. AEs may also include worsening of an existing symptom or condition or post-treatment events that occur as a result of protocol-mandated procedures.

A serious adverse event (SAE) is an AE occurring that has results in any of the following outcomes:

- Results in death
- Is life-threatening (i.e., the subject was, in the opinion of the Investigator, at immediate risk of death from the event as it occurred; it does not include an event that, had it occurred in a more severe form, might have caused death)
- Requires in-patient hospitalization or prolongation of existing hospitalization
- Results in persistent or significant disability/incapacity (i.e., substantial disruption of a person's ability to conduct normal life functions).
- Results in a congenital anomaly/birth defect in an offspring of a study subject
- Other medically significant event that, based upon appropriate medical judgment, may jeopardize the subject and may require medical or surgical intervention to prevent one of the outcomes listed above, e.g., allergic bronchospasm requiring intensive treatment in an emergency room or home, blood dyscrasias or convulsions that do not result in hospitalization, or the development of drug dependency or drug abuse.

An **unexpected adverse event (UAE)** is any AE not yet identified in nature, severity, or frequency in the current Clinical Investigators' Brochure or in the clinical safety updates.

Clinical Laboratory Changes: It is the Investigator's responsibility to review the results of all laboratory tests as they become available. For each abnormal laboratory test result, the Investigator needs to ascertain if this is a clinically significant change from baseline for that individual subject. The Investigator may repeat the laboratory test or request additional tests to verify the results of the original laboratory tests. If a laboratory value is determined to be an abnormal change from baseline for that subject, this is considered an AE.

INTENSITY

AEs will be graded on a 3-point scale and reported as indicated on the Case Report Forms. The intensity of an AE is defined as follows:

- Mild: Discomfort noticed, but no disruption to daily activity
- **Moderate:** Discomfort sufficient to disrupt normal daily activity and/or requires symptomatic treatment
- Severe: Inability to work or perform normal daily activity and requires treatment

STUDY DRUG CAUSALITY

Relationship of an AE to treatment will be assessed as follows:

- **Certain:** The AE is **clearly** related to the investigational agent(s).
- **Probably Related:** The AE is likely related to the investigational agent(s).
- **Possibly Related:** The AE may be related to the investigational agent(s).
- **Unlikely to be Related:** The AE is doubtfully related to the investigational agent(s).
- **Unrelated:** The AE is **clearly** NOT related to the investigational agent(s).
- Unassessable/unclassifiable: The AE is cannot be judged because information is insufficient or contradictory.

BACKGROUND PAH DRUG CAUSALITY

Relationship of an AE to treatment will be assessed as follows:

- **Certain:** The AE is **clearly** related to the background PAH agent(s).
- **Probably Related:** The AE is likely related to the background PAH agent(s).
- **Possibly Related:** The AE may be related to the background PAH agent(s).
- Unlikely to be Related: The AE is doubtfully related to the background PAH agent(s).
- Unrelated: The AE is clearly NOT related to the background PAH agent(s).
- Unassessable/unclassifiable: The AE is cannot be judged because information is insufficient or contradictory.

ACTION TAKEN

Action taken for an AE to treatment will be assessed as follows:

- **Study drug dose withdrawn:** Study drug administration was stopped permanently as a result of the AE.
- **Study drug temporarily discontinued:** Study drug administration was temporarily discontinued as a result of the AE.
- Study drug dose reduced: Study drug administration was reduced as a result of the AE.
- Study drug dose increased: Study drug administration was increased as a result of the AE.
- **Study drug dose not changed:** There was no alteration in either the dose or regimen of the study drug.
- Unknown: Not known what occurred with study drug administration because information is insufficient or contradictory.
- Not applicable: Not applicable.

OUTCOME

The outcome of an AE should be recorded based on the status of the AE at study completion or premature discontinuation from the study. The AE outcome would be recorded as fatal, not recovered/not resolved, recovered/resolved, recovered/resolved with sequalae, recovering/resolving or unknown. If an AE is ongoing, the AE should be followed until resolution.

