8.2.2 Phone Calls

Subject should be contacted weekly between the Baseline Visit through Week12 except for weeks with study visits, then monthly between Quarterly Visits through the end of study participation. After two weeks on study drug, the subject should be contacted to assess drug tolerability and instructed to increase the study drug dose by one tablet QID for a fixed dose of two tablets QID through the duration of the study. If a subject is unable to tolerate the two tablets QID dosing regimen, after appropriate assessment (e.g. OTC use to alleviate headache), and at the Investigator's discretion, the subject may continue in the study on one tablet QID dosing. An observed re-challenge may be attempted using the target, two tablets QID dosing, at either the Week 4 or Week 8 Visit.

During phone calls to the subject, the following information should be recorded:

- Record time and dose of study drug and inhaled treprostinil administration
- Assess and record AEs
- Record concomitant medications
- Assess clinical worsening

Subjects participating in the plasma concentration assessment should be contacted one week (seven days) prior to Week 4 and Week 12 (first Quarterly Visit) as a reminder to record their inhaled treprostinil and study drug dosing times during the week leading up to the visit.

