7.2.3 Intensity Rating

The Investigator classifies AEs into one of the following intensity categories: ‘Mild’, ‘Moderate’, and ‘Severe’ (see study protocol).

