7.2.7 Summary of Treatment-Emergent Adverse Events

A summary of all TEAEs will present numbers and percentages of the following by treatment group:

- Subjects with at least one TEAE
- Subjects with at least one IMP-related TEAE
- Subjects with at least one TEAE related to PAH background medication
- Subjects with at least one serious TEAE

- Subjects with a TEAE leading to permanent discontinuation of IMP

7.2.8 **Subjects with a TEAE leading to dose modifications of IMP Summaries of Adverse Events**

TEAEs will be separately summarized by treatment group for the following:

- Total number of TEAEs, total number subjects with at least one TEAE
- TEAEs by severity
- TEAEs by relationship to IMP
- TEAEs by relationship to PAH background medication
- TEAEs by action taken with IMP
- TEAEs leading to study withdrawal

TEAEs will be presented in alphabetical order of SOC and by decreasing order of incidence of the preferred terms.

For these summaries, a subject having the same TEAE multiple times will only be counted once for the corresponding preferred term. Similarly, a subject who experienced multiple TEAEs within the same SOC will be counted only once for that SOC.

A subject experiencing the same TEAE multiple times or at multiple severities will only be counted once under that preferred term at the worst severity rating. Similarly, a subject who experiences the same TEAE multiple times or at multiple severities across multiple preferred terms within the same SOC will only be counted once for the worst severity rating within the SOC.

A subject experiencing the same TEAE multiple times or at multiple relationships to IMP will only be counted once for the worst relationship to IMP within a preferred term. Similarly, a subject who experiences the same TEAE multiple times or at multiple relationships to IMP across multiple preferred terms within the same SOC will only be counted once for the worst relationship to IMP within the SOC. The same procedure will be used for relationship to PAH background medication.

A subject experiencing the same TEAE multiple times or at multiple actions taken to IMP will only be counted once for the worst action taken with IMP within a preferred term. Similarly, a subject who experiences the same TEAE multiple times or at multiple actions taken to IMP across multiple preferred terms within the same SOC will only be counted once for the worst action taken to IMP within the SOC.

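### Protocol Appendix 7 grades an adverse event Severe only if it is disabling and also requires treatment, so disabling events that require none fall to Moderate and the TEAE-by-severity table can under-count severe events

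*Protocol*

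**What the plan says.** Protocol Appendix 7 (Intensity) sets the scale: "AEs will be graded on a 3-point scale and reported as indicated on the Case Report Forms". Mild is noticeable discomfort without disruption. Moderate is "Discomfort sufficient to disrupt normal daily activity and/or requires symptomatic treatment". Severe is "Inability to work or perform normal daily activity and requires treatment". There is no grade above Severe, and the protocol does not define treatment.

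Appendix 7 records what was done with study drug in a separate Action Taken field. Its entries include a reduction ("Study drug administration was reduced as a result of the AE") and a permanent stop ("Study drug administration was stopped permanently as a result of the AE"). Temporary interruption has its own entry.

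For subjects who cannot tolerate the target dose, Protocol 8.2.2 says that, at the Investigator's discretion, "the subject may continue in the study on one tablet QID dosing". The same sentence first calls for an assessment and gives over-the-counter relief of headache as an example.

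SAP 7.2.3 takes over the three grades by reference to the protocol: "The Investigator classifies AEs into one of the following intensity categories". SAP 7.2.8 lists "TEAEs by severity" among the summaries by treatment group, counting a subject at the worst grade. It lists action taken with study drug as another, separate summary.

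**The concern.** On an intensity scale, a more disabling event should not receive a lower grade because it needed no remedy. Under Appendix 7 it can. Two subjects may be equally unable to function, yet the one whose event required treatment is Severe and the other is Moderate, alongside events that merely disrupted the day.

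This matters here because the response the protocol describes for intolerance includes a change to study drug, and Appendix 7 records such a change under Action Taken, not under intensity. If sites do not regard a study-drug change as treatment, incapacitating events that settle after it do not reach Severe. If some sites count it and others do not, the grade means different things at different sites. In either case the severity table may understate how often the add-on therapy is badly tolerated. SAP section 7 plans no formal testing for routine safety analyses, so a reader judges tolerability from the tables themselves.

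**Working it through.** The plan gives no figure for this point, so there is nothing to reproduce. The check is one of logic, followed by an illustration with assumed rates.

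**Step 1: the grades side by side.** Moderate joins its two conditions with and/or, so either suffices. Severe joins its two with and.

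| Event | Severe? | Grade as written |
|---|---|---|
| Incapacitating, requires treatment | both conditions met | Severe |
| Incapacitating, requires no treatment | second condition fails | Moderate |
| Disruptive only, treated or not | first condition fails | Moderate |

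The second row is the gap. Nothing else in the protocol or SAP corrects it.

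**Step 2: does a study-drug change count as treatment?** The text leaves this open. The separate Action Taken field, and the scripted probe asking whether the subject took medication for the symptom, suggest that it does not. Against that, Moderate speaks of symptomatic treatment and Severe of treatment without the adjective, which leaves room to count it.

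**Step 3: what the other tables show.** SAP 7.2.7 and 7.2.8 plan counts of TEAEs by action taken, TEAEs leading to permanent discontinuation of study drug and TEAEs leading to study withdrawal. The heading of 7.2.8 also appears to have absorbed a bullet on TEAEs leading to dose modification. A reader can therefore see, by arm, that study drug was changed, but not the grade of the events that led to the change.

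**Step 4: illustration.** Let s be the proportion of subjects with a disabling event and q the share of them whose event required no treatment under the site's reading. The recorded Severe rate is s × (1 − q). Assume s = 15% on active and 8% on placebo. The planned size is 120 per group (SAP 4.1), so this is 18 subjects against about 10. Neither s nor q is in the documents.

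| q active | q placebo | Severe, active | Severe, placebo | Difference | Ratio |
|---|---|---|---|---|---|
| 0 | 0 | 15.0% | 8.0% | 7.0 points | 1.88 |
| 25% | 25% | 15 × 0.75 = 11.25% | 8 × 0.75 = 6.0% | 5.25 points | 1.88 |
| 25% | 10% | 11.25% | 8 × 0.90 = 7.2% | 4.05 points | 1.56 |
| 50% | 20% | 15 × 0.50 = 7.5% | 8 × 0.80 = 6.4% | 1.1 points | 1.17 |
| 10% | 25% | 15 × 0.90 = 13.5% | 6.0% | 7.5 points | 2.25 |

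With equal q, both rates and the absolute difference shrink but the ratio does not. The ratio moves toward 1 only if q is larger on active, and away from 1 if q is larger on placebo. The rule lowers the count in any arm where q is above zero. What it does to the comparison depends on quantities the plan does not give.

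**The case against.** The strongest reply is that the wording gap is narrow and its consequences small. Four parts of it stand.

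- The text says requires, not received. A reader might infer that any untreated event, even an incapacitating or fatal one, becomes Moderate. The documents do not support that: an event can require treatment it never got. Death and persistent or significant disability are also serious-event criteria, independent of the intensity grade, and fatal is a recorded outcome.
- A reader might infer that every disabling event handled by a study-drug change is graded Moderate. That holds only if the site does not count the change as treatment and nothing else was required. Protocol 8.2.2 itself mentions over-the-counter relief, and a disabling headache that needed it meets both Severe conditions.
- A reader might infer that the under-count falls mainly on active drug. There is an argument for this: subjects must complete 90 days on inhaled treprostinil before randomization, so new intolerance during titration may come disproportionately from the added drug. But the documents give no rates. Both arms take inhaled treprostinil, whose listed effects overlap with those of study drug, and the lower-dose option applies to both arms under blinding.
- Events that led to a study-drug change remain visible by arm in other planned tables, and no efficacy endpoint or seriousness criterion uses the intensity grade.

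What does not stand is the suggestion that the other tables close the gap. They show the action without the severity. A short-lived incapacitating event need not meet a serious-event criterion, so serious-event reporting may not capture it either.

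**Conclusion.** The concern holds as a defect of definition. As written, a disabling event that requires no treatment is Moderate, and the SAP carries that grade into its severity table, which can under-count severe TEAEs. For events resolved by a study-drug change alone, the conclusion rests on sites not counting that change as treatment, which the protocol leaves undefined.

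The size is unknown. In the assumed example the recorded difference ranges from 1.1 to 7.5 points where the true one is 7.0, which shows only how far the answer depends on the assumptions. A larger effect on active drug is plausible but not shown. The reach is limited to descriptive safety tables. The point merits correction because the rule is explicit, nothing else corrects it, and the remedy is cheap.

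**What to change.** In Appendix 7 and the CRF completion guideline, keep the incapacity part of the Severe definition and replace its treatment clause with: whether or not treatment is required. This also removes the need to decide whether a study-drug change is treatment for the purpose of this grade. Mild and Moderate can stay as they are.

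For events already graded, add to SAP 7.2.8 a cross-tabulation of TEAE severity by action taken with study drug, by treatment group. Build it from event records, so that the grade and the action belong to the same event; the worst-grade and worst-action counts per subject cannot simply be crossed. A single row combining Severe events with any event that led to a study-drug change would be a poorer choice, because it would add mild events that prompted a change. The cross-tabulation does not regrade anything, and it cannot find disabling events that needed neither treatment nor a study-drug change. It does show how many Moderate events led to reduction, interruption or withdrawal in each arm. It could go into the addendum that SAP 6.2 already plans before unblinding.

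The cost is one line in the protocol and the CRF guideline and one table from data already collected. Severe counts would rise somewhat. If the definition changes during the study, events graded before and after the change must be identifiable so that the two are not pooled unmarked. No dose or management rule is affected.
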